### 7.1.1 Interim Analysis/Sample Size Re-estimation

An interim analysis of the PK data is planned during the trial and may be performed by an IARC on approximately 50 subjects (25 subjects per treatment group) completing the trial. In this case, completers will be defined as subjects who receive a final dose of IMP (both treatment groups) at the maximum dose. Out of the 50 subjects, approximately

Protocol 031-201-00181

14 subjects (7 subjects per treatment group) will have been enrolled to the robust sampling schedule. Subjects will continue to be enrolled into the trial until either the interim analysis is complete and recommends no sample size increase or there are enough subjects enrolled to ensure 170 completers.

If the trial is stopped due to futility (as described by the interim analysis), randomized subjects will be terminated; however, if the interim analysis stops the trial for having enough conditional power, then all randomized subjects will continue until the last observation. Subjects in screening will be discontinued and no further randomization will occur.

An alpha level of 0.001 (1-sided) is allocated to estimate the sample size during this interim analysis. The corresponding final significance level is 0.049 (1-sided).

The sample size will be re-estimated only based on the conditional power determined at the interim analysis. The adaptive designs methodology published by Chen, DeMets, and Lan (2004) will be used to increase the sample size based on an interim estimate of the treatment effect size, possibly combined with other external information, without inflating the Type I error.

All the detailed calculations and re-estimation methods will be prespecified and included in the statistical analysis plan and interim analysis plan.

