# 7 Statistical Analysis

## 7.1 Determination of Sample Size

To establish the similarity in primary PK variables, the lower bound of the 90% CI of the geometric means ratio (GMR) of  $C_{56}$  and  $AUC_{0-56}$  after the fourth dose of aripiprazole 2M LAI 960 mg to  $C_{28}$  after the eighth dose and the sum of  $AUC_{0-28}$  values after the seventh and eighth doses of aripiprazole IM depot 400 mg should be greater than 80%, respectively.

It is estimated that a total of at least 100 subjects (ie, 50 per group) completing the trial will have at least 80% power to ensure that the lower limit of the 90% CI of the GMR of  $C_{56}$  after the fourth dose of aripiprazole 2M LAI 960 mg (test) to  $C_{28}$  after the eighth dose of aripiprazole IM depot 400 mg (reference) is greater than 0.80, assuming that the actual GMR of concentrations is 1.0 and the CV is 46%.

Among these 100 subjects, at least 30 completers enrolled to the robust sampling schedule will provide at least 80% power to ensure that the lower limit of the 90% CI of the GMR of  $AUC_{0-56}$  of aripiprazole 2M LAI 960 mg (test) to the sum of  $AUC_{0-28}$  values of aripiprazole IM depot 400 mg (reference) after the seventh and eighth doses is greater than 0.80, assuming the actual GMR of concentrations is 1.15 and the CV is 40%.

The assumption of CV used in the sample calculation is based on the PK data in the previous multiple-dose aripiprazole IM depot PK Trial 31-11-298.

To ensure adequate power of the trial, an interim analysis may be conducted by the Interim Analysis Review Committee (IARC). The final sample size could be increased as per recommendation of the IARC and as further described in [Section 7.1.1](#).

Assuming a dropout rate of 34%, approximately 152 to 258 subjects will be enrolled to have 100 to 170 completers based on the recommendation of the proposed interim analysis.

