**Table 7.1.1-1      Sample Size Re-estimation**

| Endpoints   | Conditional Power | Interim Analysis Recommendation              | Outcome                             |
|---|-------------------|--|-------------------------------------|
| AUC 0-56 versus sum of AUC 0-28 values              | ≥ 80%             | No adaption to the planned sample size       | 30 completers (15 per group)        |
|   | < 80%             | Increase sample size to up to 50 completers  | Up to 50 completers (25 per group)  |
| C 56 versus C 28 after the last scheduled injection | ≥ 80%             | No adaption to the planned sample size       | 100 completers (50 per group)       |
|   | ≥ 30% and < 80%   | Increase sample size to up to 170 completers | Up to 170 completers (85 per group) |
|   | < 30%             | Stop the trial                               |                                     |

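### The rule that closes randomization after a favourable interim (Protocol 7.1.1) carries no minimum number randomised and can conflict with the planned 100 completers, 30 of them robust

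*Protocol*

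**What the plan says.** Protocol 7.1.1 gives two ways for enrolment to end. One is that it continues "until either the interim analysis is complete and recommends no sample size increase"; the other is that enough subjects are enrolled for 170 completers. If the trial stops for enough conditional power, those already randomised continue to their last observation, but "Subjects in screening will be discontinued and no further randomization will occur". Neither sentence names a minimum.

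Two nearby places describe the planned size:

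- Table 7.1.1-1 gives the recommendation at conditional power of at least 80% as "No adaption to the planned sample size". The outcomes are 100 completers for the trough comparison and 30 for AUC.
- Protocol 7.1 plans at least 100 completers, at least 30 of them robust. At 34% dropout it says "approximately 152 to 258 subjects will be enrolled to have 100 to 170 completers".

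SAP section 4 repeats the 152 to 258 range. The readable SAP text has no interim or conditional-power rule. Protocol 7.1.1 leaves the detailed methods to the SAP and an interim analysis plan.

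**The concern.** Conditional power of at least 80% in the top rows of the table is a statement about a final analysis with 100 completers (30 for AUC). If randomization closes as soon as that result is reported, the trial has that size only if about 152 subjects, about 46 of them robust, are already in. Section 7.1.1 does not require this. A sponsor could follow it to the letter and finish below the size on which both the interim decision and the stated 80% power rest.

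The robust group is the more exposed. It is recruited at only 4 to 6 sites (Protocol 3.1) and excludes current users of oral aripiprazole or the monthly depot (Protocol 3.3). Sparse-schedule subjects cannot supply AUC values. Replacement of noncompleters is at the sponsor's discretion (Protocol 3.3) and is not tied to reaching 100 and 30.

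**Working it through.** **Inputs.** From Protocol 7.1: similarity is shown when the lower 90% confidence limit of the GMR exceeds 0.80; trough GMR 1.0 with CV 46%; AUC GMR 1.15 with CV 40%; dropout 34%. From 7.1.1: interim at about 50 completers, about 14 of them robust; final one-sided level 0.049. The primary trough is taken at Day 225, 32 weeks after the first dose (SAP Table 5.2-1).

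**1. The plan's own figures reproduce.**
- Log-scale SD = √ln(1 + CV²): 0.438 for the trough, 0.385 for AUC.
- Distance from the limit: ln(1.0/0.80) = 0.223 and ln(1.15/0.80) = 0.363.
- Noncentral-t power at one-sided 0.05: 0.812 with 50 per group (trough) and 0.808 with 15 per group (AUC). At 0.049: 0.809 and 0.805.
- Dropout: 100/0.66 = 151.5, so 152; 170/0.66 = 257.6, so 258; 30/0.66 = 45.5, so 46.

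**2. Number randomised when the interim reports.** Fifty completers need 50/0.66 = 75.8, about 76 randomised. With constant accrual of r per week and an assumed 0 to 8 weeks for assay and analysis, N = 76 + 32r to 76 + 40r.
- Reaching 152 needs r = 76/32 = 2.4 with no lag, or 76/40 = 1.9 with an 8-week lag.
- r = 1.5: N = 124 to 136, so 82 to 90 completers.
- r = 1.0: N = 108 to 116, so 71 to 77 completers.
- Robust group: 14/0.66 = 21.2 randomised, so reaching 46 needs 24.8 more, or 0.62 to 0.78 per week. Twenty-two robust completers (33.3 randomised) would mean 12.1 more, or 0.30 to 0.38 per week.

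**3. Threshold case: conditional power exactly 80% at the planned size.** I assume the current-trend form, because the readable text does not specify one. With n1 interim and n final completers, f = n1/n and z_f = 1.655,

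CP(n) = Φ[(z1√f + (z1/√f)(1 − f) − z_f)/√(1 − f)].

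- Trough: CP(100) = 0.80 gives z1 = 1.591. Then CP is 0.76 at 90, 0.73 at 82, 0.71 at 77 and 0.67 at 71.
- AUC: CP(30) = 0.80 with 14 interim subjects gives z1 = 1.550. Then CP(22) = 0.68.

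**4. Average case: all interims with conditional power of at least 80%.** Under the plan's trough assumptions the interim z has mean 0.223/(0.438 × √(4/50)) = 1.80 and SD 1. At z = 1.80, CP is 0.90 at 100 completers, 0.85 at 82 and 0.82 at 71. The chance that z exceeds 1.591 is 58%. I averaged the probability of final success at the true effect over that region:

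| Trough completers | Success given the stop |
|---|---|
| 100 | 95% |
| 82 | 94% |
| 71 | 93% |

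Take the whole adaptive rule, with the increase always to 170 completers and a stop below 30%. Overall trough power is 0.774 if the favourable branch ends at 100 completers and 0.759 if it ends at 71. The same averaging for AUC (mean interim z = 0.363/(0.385 × √(4/14)) = 1.76) gives about 95% at 30 and 92% at 22.

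**The case against.** The strongest reply is that the minimum is already in the protocol. Section 7.1 ties enrolment of 152 to 258 to the interim recommendation, and the table names 100 and 30 completers as the outcome. Read with these, the closing sentence may only be meant to stop overrun while enrolment heads towards 170 completers. This stands in part. A reader might infer that the protocol plans no minimum at all, and that would be wrong. What is missing is any link between the closing rule and the minimum.

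A reader might also infer that a favourable interim generally leaves the trial with 67% to 76% power. The documents do not support that either. Those figures hold only when conditional power is exactly 80%, whereas the rule applies at 80% or more. Unconditional power at the smaller sizes does not describe trials selected for a strong interim.

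Other points that stand:
- Accrual is not given. Over about 20 sites, 1.9 to 2.4 per week is only about 0.4 to 0.5 subjects per site per month, and at that rate there is no shortfall.
- Section 7.1.1 counts as interim completers only those whose final dose was the maximum dose. More than 76 may therefore be randomised before 50 qualify.
- The interim is optional. The interim analysis plan was not available and parts of the SAP are redacted, so a floor may exist there.

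None of this reconciles the closing sentence with 7.1 and the table.

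**Conclusion.** The point holds as a conflict between passages. Followed literally, the closing rule in 7.1.1 can deliver fewer than the 100 and 30 completers that 7.1 and Table 7.1.1-1 assign to the same outcome. Whether it would do so depends on accrual below about 1.9 to 2.4 per week overall, or about 0.62 to 0.78 per week for the robust group. Both ranges assume constant accrual, 34% dropout and a lag of 0 to 8 weeks.

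The cost is modest on average: about 1 to 3 points of success among trials that stop for conditional power of at least 80%, and about 1.5 points of overall trough power at 71 completers. It is larger near the threshold: 7 to 13 points for the trough at 82 to 71 completers, and about 12 points for AUC at 22. The correction is worthwhile because the rule is ambiguous where it will be applied, and because fixing it adds nobody beyond the planned minimum.

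**What to change.** Add one clause to Protocol 7.1.1: after a no-increase recommendation, randomization continues until the planned minimum of about 152 subjects, about 46 of them on the robust schedule, has been randomised, and it closes at once only if both numbers are already reached. Align 7.1 and Table 7.1.1-1 with that wording. State that 152 and 46 are the numbers expected to give 100 and 30 completers at 34% dropout and do not guarantee them. The plan does not say how the two endpoints combine into one recommendation; this clause leaves that open.

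First check the interim analysis plan. If it already holds such a floor, a cross-reference from 7.1.1 is enough. The clause has no effect if accrual is fast. If accrual is slow, the cost is the time needed to reach the minimum already planned.

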**Table 7.1.1-1      Sample Size Re-estimation**

| Endpoints   | Conditional Power | Interim Analysis Recommendation              | Outcome                             |
|---|-------------------|--|-------------------------------------|
| AUC 0-56 versus sum of AUC 0-28 values              | ≥ 80%             | No adaption to the planned sample size       | 30 completers (15 per group)        |
|   | < 80%             | Increase sample size to up to 50 completers  | Up to 50 completers (25 per group)  |
| C 56 versus C 28 after the last scheduled injection | ≥ 80%             | No adaption to the planned sample size       | 100 completers (50 per group)       |
|   | ≥ 30% and < 80%   | Increase sample size to up to 170 completers | Up to 170 completers (85 per group) |
|   | < 30%             | Stop the trial                               |                                     |

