| Statistical Methods: | 
Determination of sample size:
 
To establish the similarity in primary PK variables, the lower bound of the 90% confidence interval (CI) of the geometric means ratio (GMR) of <math>C_{56}</math> and <math>AUC_{0-56}</math> after the fourth dose of aripiprazole 2M LAI 960 mg to <math>C_{28}</math> after the eighth dose and the sum of <math>AUC_{0-28}</math> values after the seventh and eighth doses of aripiprazole IM depot 400 mg should be greater than 80%, respectively. It is estimated that a total of at least 100 subjects (ie, 50 per group) completing the trial will have at least 80% power to ensure that the lower limit of the 90% CI of the GMR of <math>C_{56}</math> after the fourth dose of aripiprazole 2M LAI 960 mg (test) to <math>C_{28}</math> after the eighth dose of aripiprazole IM depot 400 mg (reference) is greater than 0.80, assuming the actual GMR of concentrations is 1.0 and the coefficient of variation (CV) is 46%.
 
Among these 100 subjects, 30 completers enrolled to the robust sampling schedule will provide at least 80% power to ensure that the lower limit of the 90% CI of the GMR of <math>AUC_{0-56}</math> of aripiprazole 2M LAI 960 mg (test) to the sum of <math>AUC_{0-28}</math> values of aripiprazole IM depot 400 mg (reference) after the seventh and eighth doses is greater than 0.80, assuming the actual GMR of concentrations is 1.15 and the CV is 40%.
 |
|                      | 
To ensure adequate power of the trial, an interim analysis may be conducted by the Interim Analysis Review Committee (IARC). The final sample size could be increased as per recommendation of the IARC.
 
Assuming a dropout rate of 34%, approximately 152 to 258 subjects will be enrolled to have 100 to 170 completers based on the recommendation of the proposed interim analysis.
   |
|                      | 
Primary endpoint analyses:
 
Safety assessments including AEs, vital signs, ECGs, clinical laboratory monitoring (serum chemistry, hematology, and urinalysis), physical examinations, EPS (SAS, AIMS, and BARS), VAS scores for pain perception, Investigator's Assessment of Most Recent Injection Site, and suicidality via the C-SSRS will be summarized for the safety sample by treatment group. The mean change from baseline will be provided for vital
  |

Protocol 031-201-00181

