signs, ECGs, clinical laboratory, and EPS assessments by visit, treatment group, and disease type. The incidence of clinically relevant abnormalities in vital sign, ECGs, and clinical laboratory results will be summarized descriptively by visit, treatment group, and disease type.

Plasma concentrations of aripiprazole will be analyzed using noncompartmental methods. The following PK parameters will be estimated and summarized descriptively for aripiprazole:  $C_{56}$  and  $AUC_{0-56}$  of aripiprazole 2M LAI 960 mg after the fourth dose,  $C_{28}$  of aripiprazole IM depot 400 mg after the eighth dose, and  $AUC_{0-28}$  values of aripiprazole IM depot 400 mg after the seventh and eighth doses over the course of 32 weeks. The 90% CI of GMR of  $C_{56}$  of aripiprazole after the fourth injection of aripiprazole 2M LAI 960 mg (test) to  $C_{28}$  after the eighth injection of aripiprazole IM depot 400 mg (reference) will be provided. An analysis of variance will be performed on the natural-log transformed PK parameters using the MIXED procedure in the Statistical Analysis System (SAS). The mixed-effects linear model will include treatment group, disease type (if applicable), and PK sampling schedule as fixed effects and subject as a random effect. The least squares means for the 2 treatment groups, their difference, and the 90% CI for their difference will be derived. The antilog of the confidence limits will provide the 90% CI for the GMR of the 2 treatments. For subjects enrolled to the robust sampling schedule, the values of  $AUC_{0-28}$  after the seventh and eighth dose of aripiprazole IM depot 400 mg (reference) will be summed up before analyzing by the same method together with  $AUC_{0-56}$  after the fourth injection of aripiprazole 2M LAI 960 mg (test). Only subjects who receive a fourth dose of aripiprazole 2M LAI 960 mg or a seventh and/or eighth dose of aripiprazole IM depot 400 mg and have  $C_{56}$ ,  $C_{28}$ , and  $AUC_{0-28}$  values, and  $AUC_{0-56}$  values determined for the respective treatments will be included in the analysis.

Protocol 031-201-00181

|   |   |
|---|---|

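### The AUC row of the re-estimation table has no lower conditional-power bound, so the visible text does not secure the stated type I error control; the final one-sided level is also given as both 0.049 and 0.05

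*Protocol*

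**What the plan says.** Protocol 7.1.1 plans an optional interim analysis on about 50 completers, about 14 of them (7 per group) on the robust schedule that supplies AUC. Table 7.1.1-1 then sets the sample size by conditional power:

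- **AUC row:** CP of 80% or more keeps 30 completers. Anything below 80% leads to "Increase sample size to up to 50 completers". There is no lower branch.
- **C56/C28 row:** 80% or more keeps 100 completers, 30% to below 80% allows up to 170, and below 30% stops the trial.

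The section cites a published adaptive method under which the sample size is raised "based on an interim estimate of the treatment effect size, possibly combined with other external information, without inflating the Type I error". It defers the detail: "All the detailed calculations and re-estimation methods will be prespecified and included in the statistical analysis plan and interim analysis plan".

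The visible SAP mentions the interim only in its design and sample-size text (Sections 3 and 4) and contains no re-estimation rule. The visible final analysis (Protocol 7.4.1, SAP 10.1) is an ordinary mixed model on log PK parameters, with no stage term or weights.

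On the level, 7.1.1 allocates 0.001 one-sided to the interim and 0.049 one-sided to the final analysis. The success rule in the Protocol Synopsis nevertheless uses "the lower bound of the 90% confidence interval (CI) of the geometric means ratio (GMR) of" the primary PK variables, and Protocol 7.1 and SAP 4 do the same. The analysis text, also repeated in Protocol 7.4.1 and SAP 10.1, says: "The antilog of the confidence limits will provide the 90% CI for the GMR of the 2 treatments".

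**The concern.** An unweighted final test keeps its level after an unblinded sample size increase only if increases are confined to promising interim results. If the sample is also enlarged after poor results, a chance bad start is diluted and the test gains extra opportunity to reject under the null. The C56 row excludes the poorest results; the AUC row does not.

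AUC is one of two primary PK comparisons whose lower confidence limit must exceed 0.80. Protocol 7.1.1 says without qualification that the increase does not inflate the error. In the visible text, whether that is true depends on how a number between 30 and 50 is picked and on which final statistic is used, and neither is fixed. The two values for the final level add a second, smaller ambiguity.

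**Working it through.** **Inputs.** Margin 0.80, AUC ratio 1.15, CV 40%, 30 completers (Protocol 7.1); 14 AUC completers at the interim and final level 0.049 (Protocol 7.1.1); 30 or up to 50 completers (Table 7.1.1-1); 1:1 allocation.

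**1. Reproduce the plan's power.** Log SD = sqrt(ln(1 + 0.40²)) = 0.3853. Effect = ln(1.15/0.80) = 0.3629. SE with 15 per group = 0.3853 × sqrt(2/15) = 0.1407. Power = Φ(0.3629/0.1407 − 1.645) = Φ(0.935) = 82.5%, or 80.8% with the noncentral t. The stated 80% holds.

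**2. Effect of raising N at a given interim result.** Let z1 be the interim statistic on 14 completers and c the final critical value (1.645 at 0.05). The second-stage statistic must exceed

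b(N) = (c·sqrt(N) − z1·sqrt(14)) / sqrt(N − 14),

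so the null rejection probability is 1 − Φ(b(N)). CP at the interim trend for N = 30 is 1 − Φ(b(30) − z1·sqrt(16/14)). With c = 1.645:

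| CP at N = 30 | z1 | Null rejection, N = 30 | Null rejection, N = 50 |
|---|---|---|---|
| 80% | 1.544 | 20.9% | 16.5% |
| 50% | 1.124 | 11.5% | 10.8% |
| 45% | 1.061 | 10.39% | 10.08% |
| 40.7% | 1.006 | 9.5% | 9.5% |
| 30% | 0.862 | 7.4% | 8.1% |

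The derivative of b has the sign of z1 − c·sqrt(14/N). At N = 30 it is zero at z1 = 1.645 × sqrt(14/30) = 1.124, which is exactly CP 50%. From there up, every increase lowers null rejection. Going all the way to 50 lowers it down to CP of about 41%. Increases at lower CP raise it. Under the null, CP is below 50% in about 87% of interims (Φ(1.124)).

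**3. Overall one-sided error** at a true ratio of 0.80, integrating over z1 (normal theory; CV cancels):

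| Rule when CP < 80% | 90% CI | 0.049 |
|---|---|---|
| Raise only if 80% CP is reachable by 50, else 30 | 4.94% | 4.84% |
| Always 50 | 5.63% | 5.52% |
| To the 80%-CP size, capped at 50 | 5.70% | 5.59% |
| Lowest over any N in 30–50 | 4.84% | 4.74% |
| Highest over any N in 30–50 | 5.80% | 5.69% |
| 30% bound, N = 50 if raised | 4.85% | 4.75% |
| 30% bound, highest over any N | 5.02% | 4.92% |
| 50% bound, highest over any N | 5.00% | 4.90% |
| Fixed stage weights | 5.00% | 4.90% |

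Simulation with t-tests agrees: always 50 gives 5.61% to 5.67% with the 90% CI across runs.

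**4. Sensitivity.** With 10 to 20 AUC completers at the interim, the highest figure is 5.6% to 6.1% (90% CI). If every path ends with at least 40 AUC completers it falls to 5.3%; at 50 it is nominal. If CP is computed at the planned ratio of 1.15 instead of the interim estimate, the highest figure at 0.049 is 5.42% with a 30% bound and 5.10% with a 50% bound, so the definition of CP matters.

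**5. Level.** One-sided 0.049 corresponds to a CI of 1 − 2 × 0.049 = 90.2%, about 0.6% wider than the 90% CI.

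**The case against.** The strongest objection is that the deciding text cannot be seen. Section 7.1.1 names a published method and promises the detail in the SAP and an interim analysis plan. That plan is not supplied and parts of the SAP are redacted. This stands: the claim can only be about the visible text. A reader might infer that the trial's type I error is inflated or that no rule for N exists. The documents support neither.

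A reader might also take 5.8% as the plan's error rate. That figure needs N to be chosen, at each interim result, so as to maximise false rejection, and no text describes such a rule. The direct readings give 5.6% to 5.7%, and one reasonable reading gives 4.9%.

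The excess may also be smaller in practice. Enrolment does not pause: "Subjects will continue to be enrolled into the trial until either the interim analysis is complete and recommends no sample size increase", or until enough are enrolled for 170 completers. The no-increase path may therefore end above 30 AUC completers. Both endpoints must pass, and the C56 stop removes some trials. With AUC at 0.80, the C56 stop binding, the highest-error N and an assumed AUC/C56 correlation of 0 to 0.9, the chance of passing both (90% CI) is 4.5% to 5.4% at the planned C56 ratio of 1.0 and 2.1% to 3.9% at 0.90. It is 5.7% to 5.8% at 1.15, so the C56 stop is not reliable protection for AUC.

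Finally, it is tempting to say that the mismatch between 0.049 and the 90% CI itself pushes the error above 5%. It does not: the table has no early-success branch, so a 90% CI without adaptation stays at 5%. Nor does using 0.049 remove the excess.

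**Conclusion.** The AUC row lacks the lower bound that the C56 row has. Under the two most direct readings of the rule, the visible unweighted test has a one-sided error of about 5.6% to 5.7% with the 90% CI, or 5.5% to 5.6% at 0.049. This rests on the interim being run, 14 interim AUC completers, CP at the interim trend, AUC viewed alone, and 30 completers without an increase. The visible text does not secure the control that 7.1.1 asserts; unseen text may. The two final levels are a separate inconsistency with no inflation of its own. Severity is minor to moderate: the excess is at most about 0.8 points, but it concerns a primary endpoint and is inexpensive to close.

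**What to change.** 1. **Close the AUC rule**, in one of three ways:
   - Split the row: increase to up to 50 completers only if CP is at least 30% and below 80%; below 30%, no increase (planned 30 completers). State in 7.1.1 that CP for this rule is computed at the interim estimate. With the final test at 0.049 this holds the error at or below 4.92% for any N from 30 to 50. A 50% bound is needed only if the 90% CI is kept and N is left free, where a 30% bound gives 5.02%.
   - Keep the row and state in Protocol 7.4.1 and SAP 10.1 that AUC is tested after an interim with fixed stage weights (sqrt(14/30) and sqrt(16/30) for 14 interim completers), with the CI from inverting that test.
   - If the interim analysis plan already fixes the N rule or the statistic, cite it in 7.1.1 and SAP 10.1.
2. **State one success level** in the Synopsis, Protocol 7.1 and SAP 4, and carry it to the analysis text: 90% CI if no interim is performed, 90.2% CI (one-sided 0.049) if it is.

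**Cost.** No added subjects or visits, but the first option changes the adaptation rule. At a ratio of 1.15, CV 40% and level 0.049 (normal theory), AUC power falls from about 93% under always 50 to about 86% with a 30% bound or 85% with a 50% bound when N goes to 50. If N is barely raised it is close to the 30-completer power, 82.3% (80.5% by t), still above the stated 80%. Fixed stage weights keep about 91% to 92% but need a less familiar CI.
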